Clinical Trial Protocol

**Title : Immediate versus Deferred
Cytoreductive Nephrectomy with
Ipilimumab/Nivolumab in Metastatic
Clear Cell Renal Cell Carcinoma: A
Multicenter, Randomized, Open-Label
Phase III Trial**

Principal Investigator:

**[name], PhD
(Seoul National University Hospital)**

Document date : 12th, August, 2025

Study Objectives

The primary objective of this trial is to establish the optimal treatment strategy for patients with synchronous metastatic clear cell renal cell carcinoma (mRCC) in the era of immune checkpoint inhibitors by comparing upfront versus deferred cytoreductive nephrectomy (CN) combined with ipilimumab and nivolumab.

Study Design

This is a multicenter, randomized, open-label, phase III clinical trial conducted at 12 sites in Korea. A total of 172 participants with IMDC intermediate- or poor-risk mRCC will be randomized 1:1 to either upfront CN followed by ipilimumab/nivolumab induction and nivolumab maintenance, or ipilimumab/nivolumab induction followed by deferred CN and nivolumab maintenance. Participants will be followed for 15 months.

Arms and Interventions

Arm A (Experimental): Upfront CN → 4 cycles ipilimumab/nivolumab → nivolumab maintenance

Arm B (Experimental): 4 cycles ipilimumab/nivolumab → Deferred CN → nivolumab maintenance

Primary Outcome Measure

Progression-Free Survival (PFS): Time from randomization to first documented disease progression or death from any cause, assessed up to 15 months.

Secondary Outcome Measures

- Overall Survival (OS)
- Surgical morbidity (Clavien-Dindo classification, CTCAE v4.0)
- Radiologic tumor response (RECIST v1.1)
- Rate of unresectable tumors in deferred CN arm
- Effect of CN on early progression (within 4 weeks post-surgery)
- Comparison of surgical approach and extent
- Quality of life (QoL) assessments

Eligibility Criteria

Inclusion: Adults ≥ 19 years, histologically confirmed synchronous clear cell mRCC, IMDC intermediate- or poor-risk, ECOG 0–1, measurable metastatic lesion, resectable primary tumor, life expectancy >3 months, informed consent.

Exclusion: Prior systemic therapy for mRCC, other malignancy within 2 years, significant uncontrolled comorbidities, autoimmune disease, chronic immunosuppressive therapy, or deemed unsuitable by investigator.

Sample Size

A total of 172 participants (86 per arm) are required to detect a difference in PFS between arms, assuming 15-month PFS of 72% in upfront CN vs 87% in deferred CN, with 80% power and a two-sided alpha of 0.05.

Safety Assessments

Safety will be monitored through perioperative complication rates and immune-related adverse events (irAEs) associated with ipilimumab/nivolumab. Monitoring will follow CTCAE v5.0 and Clavien-Dindo classification.

Study Methods

1. Institutional Review Board (IRB) approval will be obtained from all participating institutions. The coordinating institution (Seoul National University Hospital) will establish a Data Management Plan and Data Quality Control plan, and will implement a randomization system and electronic case report form (eCRF) system. Randomization schedules will be generated by the Medical Research Collaborating Center (MRCC) using a web-based permuted block randomization approach. The coordinating institution will conduct data monitoring and external audits through its Clinical Trials Center.
2. **Enrollment:** Eligible patients with metastatic renal cell carcinoma (intermediate or poor risk) will be identified during outpatient visits. The investigator or sub-investigator will provide sufficient explanation and obtain written informed consent.
3. A biopsy of the renal mass will be performed to confirm clear cell RCC.

4. **Pre-treatment evaluations and procedures:** Baseline tests and perioperative care will be performed identically in both Arm A (Deferred CN) and Arm B (Upfront CN).
5. **Randomization:** Randomization will be performed immediately after screening using permuted block randomization, stratified by IMDC intermediate vs poor risk group. This study is conducted in an open-label design.
6. **Interventions:** Participants will follow the treatment schedule according to their randomized group.
 - **Upfront CN Arm:** Patients will undergo upfront cytoreductive nephrectomy. Peripheral blood mononuclear cells (PBMCs) will be collected preoperatively, postoperatively, and after completion of 4 cycles of ipilimumab/nivolumab. Four weeks after surgery, perioperative complications and progression status will be evaluated. Based on these findings, patients will receive 4 cycles of ipilimumab/nivolumab induction within 6 weeks after surgery, followed by assessment of progression status, safety, and quality of life (QoL). Thereafter, maintenance nivolumab will be administered with assessments every 3 months. At 15 months after treatment initiation, progression and survival status will be determined.
 - **Deferred CN Arm:** Patients will receive 4 cycles of ipilimumab/nivolumab induction therapy. PBMCs will be collected before and after induction. Following induction, progression status, safety, and QoL will be assessed, after which deferred cytoreductive nephrectomy will be performed. Additional PBMCs will be collected after surgery. Four weeks postoperatively, perioperative complications and progression status will be evaluated. Thereafter, nivolumab maintenance will be given with assessments every 3 months. At 15 months after treatment initiation, progression and survival status will be determined.

Additional Considerations:

- If progressive disease (PD) is observed during induction therapy, this will be defined as the progression event for the primary endpoint. At the investigator's discretion, patients may switch to second-line systemic therapy or undergo CN.
- For patients with response or stable disease (complete response, partial response, or stable disease), CN will be planned after induction therapy (approximately 3 months). However, considering potential clinical or logistical delays, a window period of up to 3.5 months after completion of induction will be allowed for surgery. During this window, additional nivolumab maintenance therapy may be administered.

9. **Perioperative management and documentation:** Pre- and post-surgical management and documentation will be standardized across both study arms.

10. Follow-up: Participants will be followed for 15 months from treatment initiation. Data will be collected at each immunotherapy cycle and during follow-up visits, with additional perioperative outcomes collected for 3 months post-surgery.

Data and Safety Monitoring

The study will be monitored by a centralized Data and Safety Monitoring Committee. Data will be collected via electronic CRFs and managed under secure conditions with quality control oversight.

Expected Impact

This trial will provide high-level evidence on the role and optimal timing of CN in the era of immunotherapy for mRCC, inform treatment guidelines, and improve patient survival and quality of life.

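### 172 participants followed to month 15 give about 35 PFS events and about 70% power on the protocol's own rates, not the stated 80%

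*Protocol*

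**What the plan says.** Under Primary Outcome Measure, PFS is "Time from randomization to first documented disease progression or death from any cause, assessed up to 15 months". Under Study Methods, item 10 (Follow-up), the limit applies to each participant: "Participants will be followed for 15 months from treatment initiation". The description of each arm under Interventions ends the same way: "At 15 months after treatment initiation, progression and survival status will be determined".

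The Sample Size section fixes the number: "A total of 172 participants (86 per arm) are required to detect a difference in PFS between arms". It gives the planning rates for this as "assuming 15-month PFS of 72% in upfront CN vs 87% in deferred CN". The error rates there are a two-sided 5% significance level and 80% power.

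The protocol gives no required or expected number of events, accrual period, dropout rate, common data cut-off, or PFS assumption beyond month 15. For deferred nephrectomy, surgery is planned after about 3 months of induction, and "a window period of up to 3.5 months after completion of induction will be allowed for surgery".

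**The concern.** PFS is a time-to-event endpoint, and the precision of its hazard ratio depends on the number of events. If progression is assessed only to month 15, the planning rates leave 72% and 87% of participants event-free. About 80% of the sample then contributes no event. The question is whether the remaining events support the stated power. If they do not, the sponsor, the ethics committees and the monitoring committee are relying on a power figure that the trial does not have, and a true difference of the planned size would be missed more often than stated.

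**Working it through.** **Inputs, all from Sample Size and Primary Outcome Measure:** 86 per arm; 15-month PFS 0.72 (upfront) and 0.87 (deferred); two-sided alpha 0.05; power 80%; assessment to month 15.

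**1. Can 172 be reproduced?** Comparing two proportions with unpooled variance, n per arm = (z_α + z_β)² × (0.72×0.28 + 0.87×0.13) / 0.15².
- Two-sided 0.05: (1.960 + 0.8416)² = 7.849; 7.849 × 0.3147 / 0.0225 = 109.8, so 110 per arm and 220 in total. Other versions give 226 (pooled), 222 (arcsine) and 252 (continuity-corrected).
- One-sided 0.05: (1.645 + 0.8416)² = 6.183; 6.183 × 0.3147 / 0.0225 = 86.5 per arm, so 174 in total when rounded up.

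The stated 172 is therefore not reproduced at two-sided 0.05. It lies close to a one-sided 0.05 calculation.

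**2. Expected events by month 15.** 86 × 0.28 + 86 × 0.13 = 24.1 + 11.2 = 35.3, a mean event probability of 0.205.

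**3. Required events.** Under proportional hazards, HR = ln(0.87)/ln(0.72) = 0.424 and ln(HR) = −0.858.
- Schoenfeld: 4 × 7.849 / 0.858² = 42.6, so 43 events, or 43/0.205 = about 210 participants.
- Freedman: 7.849 × (1.424/0.576)² = 48.0, so 48 events, or 48/0.205 = about 235 participants.

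**4. Power with 35.3 events.**
- Schoenfeld: Φ(√35.3 × 0.858/2 − 1.96) = Φ(0.59) = 72%.
- Freedman: Φ(√35.3 × 0.576/1.424 − 1.96) = Φ(0.44) = 67%.
- Comparison of proportions with 86 per arm: 69%.
- Simulated log-rank test: 70%.

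Dropout lowers these further. With 10% lost by month 15, 33.5 events are expected and power is 70% (Schoenfeld) or 65% (Freedman).

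**5. What a common cut-off could add.** Suppose all 172 are followed until the last one randomized reaches month 15. Assume uniform accrual over A months, constant hazards (−ln 0.72/15 = 0.0219 and −ln 0.87/15 = 0.00928 per month) and no dropout. Expected events are then 86 times the sum over arms of the mean of 1 − S(15 + u), with u uniform on 0 to A. Accrual is not stated, so a range is shown.

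| A (months) | Events | Power, Schoenfeld | Power, Freedman |
|---|---|---|---|
| 6 | 41.2 | 79% | 74% |
| 9 | 44.0 | 81% | 77% |
| 12 | 46.7 | 83% | 79% |
| 18 | 51.9 | 87% | 83% |
| 24 | 56.8 | 90% | 86% |
| 36 | 65.6 | 94% | 91% |

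The required events are reached with about 8 months' accrual (43 events) or 13.5 months' (48 events). With 10% loss by month 15, power is 81% / 76% at A = 12, 84% / 80% at 18 and 87% / 83% at 24.

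**6. Sensitivity to what happens after month 15.**
- Both hazards halve and the HR is unchanged: Schoenfeld power is 76%, 79%, 81%, 83% and 87% for A = 6, 12, 18, 24 and 36.
- Later HR 0.7: simulated power stays near 70% for A = 12 to 36, no better than the present plan.
- Later HR 1.0: simulated power falls to about 55% or a little less at A = 12, 43% at A = 24 and 38% at A = 36.

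**The case against.** The strongest reply is that the horizon is not at fault. The endpoint, the sizing rates, the final status determination and the follow-up period all use 15 months, and equal fixed follow-up is a legitimate design. With about 210 to 235 participants the same horizon would give 80% power. This stands: the shortfall arises because 172 does not match a two-sided 0.05 test, not because observation stops at month 15. For the same reason it would be wrong to say that the plan discards events. Later events are simply not collected.

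A reader might infer that a common cut-off would recover the 80%. The protocol does not support that without conditions. It states neither accrual nor any PFS assumption after month 15, and if the benefit wanes, added follow-up leaves power unchanged or lowers it.

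A reader might also infer a bias against one arm. Surgery at about 3 to 3 + 3.5 = 6.5 months leaves 15 − 6.5 = 8.5 to 15 − 3 = 12 months after deferred nephrectomy, against nearly 15 in the upfront arm. But PFS runs from randomization in both arms and the later surgery is the strategy under test, so the comparison is over equal time. A common cut-off leaves the surgical lag unchanged, and the last entrants would still have only 8.5 to 12 months after surgery. This limits interpretation; it is not a bias that the cut-off removes.

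Finally, the closeness of 172 to a one-sided calculation does not show how the sponsor derived it. The protocol says two-sided.

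**Conclusion.** The point holds as a misstatement of power. On the protocol's own rates, 172 participants assessed to month 15 give about 35 PFS events against about 43 to 48 needed, so power is about 67 to 72% and not 80%. The proportions calculation and the log-rank simulation fall in the same range, so the finding does not depend on which test the analysis plan specifies. It rests on the stated rates, no dropout and, for the event-based figures, proportional hazards; dropout makes it worse. The protocol counts PFS from randomization but follow-up from treatment initiation, so the months available after surgery shift slightly with any delay to treatment start.

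The common cut-off is an option and not a required correction. Its gain depends on the accrual period and on an HR of about 0.42 largely persisting after month 15.

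**What to change.** In the Sample Size section, state the method, the HR of 0.424, the required events (43 by Schoenfeld, 48 by Freedman) and the expected events (about 35), and restate the power for 172 participants with 15-month follow-up as about 70%. Add the accrual and dropout assumptions. This costs only protocol wording.

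To raise power without more patients, the sponsor can keep progression-free participants on the 3-monthly assessments until the last randomized participant reaches month 15 from randomization. All PFS time would enter the primary analysis, and 15-month PFS would be kept as a Kaplan-Meier estimate. The Primary Outcome Measure and item 10 would need matching changes. Before adopting this, the sponsor should show the expected power for its projected accrual, with and without a waning effect.

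The cost is real. With uniform accrual over 24 months, participants still progression-free at month 15 would have about 24/2 = 12 further months of follow-up on average. The imaging should be scheduled, because irregular late assessment of progression would be a weakness in an open-label trial. The last participant's month 15 is not delayed. The alternative is to keep the 15-month horizon and enlarge the sample to about 210 to 235, more with dropout.

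### Do the two CTCAE versions named in the protocol leave the grading of surgical morbidity unsettled?

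*Protocol*

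**What the plan says.** CTCAE appears twice in the protocol, with a different version each time.

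- **Secondary Outcome Measures:** "Surgical morbidity (Clavien-Dindo classification, CTCAE v4.0".
- **Safety Assessments:** "Safety will be monitored through perioperative complication rates and immune-related adverse events (irAEs", followed in the next sentence by "Monitoring will follow CTCAE v5.0 and Clavien-Dindo classification".

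The perioperative provisions under Study Methods name no version. Complications are assessed four weeks after surgery in each arm. Item 9 states "Pre- and post-surgical management and documentation will be standardized across both study arms". Item 10 sets a longer collection period for surgical outcomes: "with additional perioperative outcomes collected for 3 months post-surgery". Study Methods item 1 also provides for a data management plan, a data quality control plan and an eCRF system, none of which is part of the document reviewed here.

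**The concern.** Surgical morbidity is a named secondary outcome, and CTCAE grade is one of its two scales. The safety section puts perioperative complications within its scope and then names a different CTCAE version from the one attached to the outcome. Read literally, one postoperative complication could be graded on v4.0 for the outcome and on v5.0 for safety monitoring. The protocol has no sentence that assigns each version to a class of events or says that events are graded twice.

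If sites resolved this differently, CTCAE grades could be mixed across the 12 centres. The surgical morbidity table and the perioperative part of the safety report might then disagree on the same events. If the mixture also differed by arm, the comparison of morbidity between upfront and deferred nephrectomy would be affected.

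**Working it through.** No arithmetic applies: the point depends on no sample size, power, alpha or event count. The check is to set the two statements side by side and ask what follows from each reading.

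| Place in protocol | Events in scope | Scales named |
|---|---|---|
| Secondary Outcome Measures | Surgical morbidity | Clavien-Dindo, CTCAE v4.0 |
| Safety Assessments | Perioperative complications and immune-related events | CTCAE v5.0, Clavien-Dindo |

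**Step 1: is the outcome's version fixed?** Yes. The line that defines the outcome names v4.0. The safety section describes monitoring and does not redefine a secondary outcome. Only the reach of v5.0 within safety monitoring is open.

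**Step 2: the paired reading.** The safety section names two event types and two scales. Clavien-Dindo grades surgical complications, so it pairs naturally with the perioperative events and leaves CTCAE v5.0 for the immune-related events. No complication is then graded on both versions. The trial uses v4.0 for surgical morbidity and v5.0 for drug toxicity.

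**Step 3: the joint reading.** If both scales apply to both event types, a perioperative complication has a v4.0 grade for the outcome and a v5.0 grade for monitoring. That is redundant, but the outcome table still uses v4.0 and the monitoring report still uses v5.0, each for both arms.

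**Step 4: could the version differ by arm?** Neither statement distinguishes the arms. The four-week evaluation is worded to the same effect for upfront surgery ("Four weeks after surgery, perioperative complications and progression status will be evaluated") and for deferred surgery ("Four weeks postoperatively, perioperative complications and progression status will be evaluated"), and item 9 requires common documentation. A like-for-like comparison needs the same version in both arms, and the text gives no route to a different one.

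**Step 5: what else depends on CTCAE?** Clavien-Dindo is named in both places and is unaffected. The primary endpoint is progression or death, and the sample size rests on 15-month progression-free proportions. Neither uses a CTCAE grade.

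**Step 6: can an effect be sized?** No. That would need the frequency of perioperative events and the proportion whose grade changes between versions, and the protocol gives neither. The 172 randomised participants are not a useful upper bound. Only those with a gradable perioperative event matter, and not all will have surgery: nephrectomy is discretionary after progression during induction, and the rate of unresectable tumours in the deferred arm is itself an outcome.

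**The case for a change.** The strongest case for acting is that the paired reading still leaves two versions in one trial, and so needs a rule for sorting events. Surgical and drug events share a time window. In the upfront arm, induction starts within 6 weeks of surgery while perioperative outcomes are collected for 3 months. In the deferred arm, surgery follows induction and is followed by nivolumab, which may also be given while awaiting surgery. A complication in that window could be attributed to surgery or to drug, and its version would follow from the attribution. A further argument is that the protocol itself states both versions, so a statistical analysis plan that chose one would still disagree with one protocol statement. The correction would be a single word.

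Part of this stands. The numbers do differ, nothing reconciles them, and alignment would be cheap. The attribution argument carries less weight. Deciding whether an event is surgical is needed for the surgical morbidity outcome whichever version is used, and one common version would not remove that task. Once an event is counted as surgical morbidity, v4.0 applies in either arm.

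The silence of the visit schedule and of the data-handling statement ("Data will be collected via electronic CRFs and managed under secure conditions with quality control oversight") adds nothing, since such lines would not be expected to repeat a grading version. The grading field itself belongs in the eCRF specification and data management plan, which cannot be assumed to leave it unset.

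**Conclusion.** The inconsistency is genuine but editorial. Followed as written, the plan grades surgical morbidity on Clavien-Dindo and CTCAE v4.0 in both arms and monitors safety under CTCAE v5.0 and Clavien-Dindo. No result, comparison between arms or conclusion is shown to be wrong under either reading of the safety section. There is no effect on progression-free survival, the sample size or Clavien-Dindo grading, and any effect on the CTCAE grades cannot be quantified from the protocol.

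This conclusion rests on two assumptions: that the line defining the outcome governs its grading, and that the eCRF applies one version per use across sites and arms, as the commitment to common documentation implies. It would change only if there were evidence that sites or arms graded the same outcome on different versions, and the protocol contains none. Aligning the version number would tidy the text but brings no demonstrable gain to the trial's inference, so no change is called for.

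### The unresectability outcome is defined in the deferred arm only, so it cannot separate resectability lost while waiting from misjudgement at screening; the same outcome should be reported in both arms

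*Protocol*

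**What the plan says.** The Study Objectives seek the best strategy "by comparing upfront versus deferred cytoreductive nephrectomy (CN) combined with ipilimumab and nivolumab". The Eligibility Criteria require, of all participants, a "measurable metastatic lesion, resectable primary tumor, life expectancy >3 months, informed consent". Study Methods item 5 places randomization directly after screening, and the Study Design allocates 1:1.

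Under Secondary Outcome Measures, unresectability appears once, as "Rate of unresectable tumors in deferred CN arm". The same list contains "Comparison of surgical approach and extent", which is not tied to one arm.

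On conduct, the upfront-arm text in Study Methods says "Patients will undergo upfront cytoreductive nephrectomy" and does not say how an operation that is not done or not completed is classified. In the deferred arm, CN is planned after induction for patients with response or stable disease, with a window of up to 3.5 months after induction ends. For patients who progress during induction, Additional Considerations says "At the investigator's discretion, patients may switch to second-line systemic therapy or undergo CN". Study Methods item 9 adds: "Pre- and post-surgical management and documentation will be standardized across both study arms".

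**The concern.** In the deferred arm, a primary that proves unresectable may have become so between screening and the planned operation, or the screening judgement may have been wrong from the start. Only the first is a consequence of deferral. The upfront arm has the same entry criterion and is operated on without induction beforehand, so it shows how often the screening judgement fails by itself. Restricting the outcome to the deferred arm sets aside a randomized comparator that the trial already has.

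Whether waiting costs some patients their operation bears directly on a trial that compares upfront with deferred CN. As written, the answer will be a single-arm percentage with no randomized contrast, and readers will have to guess how much of it to attribute to deferral.

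**Working it through.** **What the two designs estimate.** Let m be the proportion of primaries judged resectable at screening that would prove unresectable at immediate operation, and c the net change in that proportion caused by deferring. Randomization makes m the same in both arms in expectation.

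- Deferred arm: D = m + c
- Upfront arm: U = m
- Difference: D − U = c

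The listed outcome estimates D. It equals c only if m = 0. The protocol gives no value for m, and D alone cannot supply one. The term c is a net effect and may have either sign, since some tumours may become easier to remove during induction.

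**Inputs.** The 86 per arm is taken from the Sample Size section as stated; whether that number suffices for PFS is a separate matter. The protocol states no rate, precision or power for unresectability, so there is no figure to reproduce. All rates below are assumptions.

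**Single arm of 86, exact (Clopper-Pearson) 95% CI:**

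| Unresectable | Rate | 95% CI |
|---|---|---|
| 0 | 0% | 0 to 4.2% |
| 4 | 4.7% | 1.3 to 11.5% |
| 9 | 10.5% | 4.9 to 18.9% |
| 13 | 15.1% | 8.3 to 24.5% |

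**Two arms of 86, precision of the difference.** Half-width = 1.96 × √[p₁(1 − p₁)/86 + p₂(1 − p₂)/86]. For assumed rates of 5% and 8%: √[(0.0475 + 0.0736)/86] = √0.001408 = 0.0375, and 1.96 × 0.0375 = 0.074, or about ±7 points.

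**Two arms of 86, power at two-sided 0.05.** The normal approximation is Φ{[|p₂ − p₁|√86 − 1.96√(2p̄(1 − p̄))] / √[p₁(1 − p₁) + p₂(1 − p₂)]}, with p̄ the mean of the two rates. For example, 5% vs 20% gives (1.391 − 0.917)/0.456 = 1.04, so 85%.

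| Upfront vs deferred (assumed) | Gap | CI half-width | Power, normal approx. | Power, Fisher exact |
|---|---|---|---|---|
| 2% vs 5% | 3 | ±5.5 | 19% | 7% |
| 2% vs 10% | 8 | ±7.0 | 60% | 49% |
| 2% vs 15% | 13 | ±8.1 | 87% | 86% |
| 5% vs 10% | 5 | ±7.8 | 24% | 16% |
| 5% vs 15% | 10 | ±8.8 | 59% | 52% |
| 5% vs 20% | 15 | ±9.6 | 85% | 83% |

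Among these scenarios, the smallest gaps that pass 80% power are 13 points (from 2%) and 15 points (from 5%). The comparison removes the confusion with screening error, but it is imprecise and should be presented as an estimate with its interval.

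**The case against.** A single-arm feasibility rate is a legitimate descriptive outcome, and the protocol contradicts nothing by listing one. Every patient is judged resectable at entry, so the deferred-arm rate is already a change from a baseline of none. If screening misjudgement is rare, the rate is nearly clean. Surgical documentation is standardized across arms and surgical extent is compared, so failed or incomplete upfront operations could probably be found in the records. A two-arm comparison would not resolve a small difference in any case.

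Most of this stands, and it limits the point. It does not remove it. Nothing in the protocol shows that misjudgement is rare. Standardized documentation around surgery does not ensure that the reason is captured when no surgery takes place. A contrast specified in advance is also more credible than one assembled afterwards in an open-label trial.

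Three stronger readings are tempting and are not supported:

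- **That the trial cannot say whether deferral costs resectability.** The deferred rate does inform on this, given the common entry criterion. What it cannot do alone is apportion the cause.
- **That the rate will leave out patients who progress during induction, up to 13% of the arm.** The 13% is the complement of the assumed 87% PFS at 15 months. It counts all progressions and deaths over the whole period, and a planning assumption is not a ceiling on progression during induction. Those patients may still undergo CN, and the protocol does not say that the rate is taken at planned surgery. The denominator alone is a detail that an SAP may settle.
- **That a specific share of any deferred-arm rate is due to screening error.** The documents give no misjudgement rate from which to calculate it.

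**Conclusion.** The point holds as a minor improvement to one secondary outcome. As worded, the outcome estimates resectability lost before the deferred operation plus error in the screening judgement. Adding the upfront arm isolates the net effect of deferral by randomization. The size of the contamination is unknown. The gain is in interpretation more than precision, given the wide intervals above. The conclusion rests on the common entry criterion, on randomization directly after screening, and on 86 patients per arm. It has no bearing on PFS, OS or the sample size.

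**What to change.** Reword the secondary outcome as the proportion of all randomized patients, in each arm, whose assigned CN was not done or not completed because the primary was unresectable. Use one definition of unresectable for both arms.

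Add one eCRF item, identical in both arms, for the reason that any assigned CN was not completed: unresectable, progression, toxicity or unfit, death, refusal, or no residual disease.

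Report the between-arm difference in unresectability with a 95% CI, labelled descriptive. Tabulate the other reasons by arm beside it, so that a reader can see how many patients never reached a judgement of resectability. Do not test a pooled total of non-completion: it would mix a favourable reason (no residual disease) with unfavourable ones, and the deferred arm has longer in which to miss surgery.

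The cost is a wording change and a slightly longer form, with no change to sample size, treatment or visits. The item should be in place before enrolment, since reasons for missed surgery are hard to recover later.

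### With 86 patients per arm, power for 72% versus 87% 15-month PFS at two-sided 0.05 is about 70%, not the stated 80%

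*Protocol*

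**What the plan says.** The Sample Size section of the protocol states: "A total of 172 participants (86 per arm) are required to detect a difference in PFS between arms". The inputs follow in the same sentence: "assuming 15-month PFS of 72% in upfront CN vs 87% in deferred CN, with 80% power and a two-sided alpha of 0.05". The Study Design section repeats the total ("A total of 172 participants with IMDC intermediate- or poor-risk mRCC will be randomized 1:1") and fixes the observation period: "Participants will be followed for 15 months". The primary outcome is PFS as a time-to-event measure from randomization, assessed up to 15 months. The protocol states no test, hazard ratio, event count or loss rate for this calculation.

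**The concern.** Sample size, allocation, both event-free rates, power and alpha are all given, so the calculation can be repeated without any outside figure. When it is repeated, 86 per arm falls well short of what the other inputs require. This sentence is the only justification for the size of a phase III trial whose stated aim is high-level evidence to inform treatment guidelines. If the power is overstated, a null result will be read as coming from a trial with a 20% risk of missing the design effect when the risk is nearer 30%. If the power is right, the stated alpha is wrong, and readers will assume a stricter type I error rate than the one used.

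**Working it through.** **Inputs (Sample Size and Study Design sections).** n = 86 per arm, 1:1; p₁ = 0.72 (upfront CN); p₂ = 0.87 (deferred CN); power 80%; alpha 0.05 two-sided; 15 months of follow-up. Normal quantiles: 1.960 (two-sided 0.05), 1.645 (one-sided 0.05), 0.842 (80% power). Hence (1.960 + 0.842)² = 7.849 and (1.645 + 0.842)² = 6.183.

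**Attempt to reproduce 86 per arm at two-sided 0.05**

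- *Two proportions, unpooled variance.* n = 7.849 × [p₁(1−p₁) + p₂(1−p₂)] / (p₂−p₁)² = 7.849 × (0.2016 + 0.1131) / 0.0225 = 109.8, so 110 per arm.
- *Two proportions, pooled variance.* The mean proportion is 0.795. n = [1.960√(2 × 0.795 × 0.205) + 0.842√0.3147]² / 0.0225 = 112.5, so 113 per arm.
- *Arcsine.* 110.2, so 111 per arm.
- *Log-rank, Schoenfeld.* Under proportional hazards, HR = ln 0.87 / ln 0.72 = 0.424 and (ln HR)² = 0.7365. Events = 4 × 7.849 / 0.7365 = 42.6. The mean event probability by 15 months is (0.28 + 0.13)/2 = 0.205, so the total is 42.6 / 0.205 = 208.
- *Log-rank, Freedman.* Events = 7.849 × [(1 + 0.424)/(1 − 0.424)]² = 48.0, total 234.

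None of these gives 172. The smallest, 208, is 21% larger (208/172 = 1.21).

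**Power at 86 per arm**

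Expected events by 15 months: 172 × 0.205 = 35.3.

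| Method | Two-sided 0.05 | One-sided 0.05 |
|---|---|---|
| Two proportions, pooled | 68.6% | 79.0% |
| Two proportions, unpooled | 69.8% | 79.8% |
| Chi-square test, exact binomial power | 69.1% | 79.8% |
| Log-rank, Schoenfeld | 72.2% | 81.7% |
| Log-rank, Freedman | 67.1% | 77.6% |
| Complementary log-log at 15 months | 65.8% | 76.5% |
| Log-rank, simulated (20,000 runs, exponential PFS, censored at 15 months) | 69.8% | 80.5% |

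Fisher's exact test at two-sided 0.05 gives 62%.

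**Where 86 might come from.** At one-sided 0.05 the unpooled formula gives 6.183 × 0.3147 / 0.0225 = 86.5 per arm, and arcsine gives 86.8. The pooled formula gives 88.5, and Schoenfeld gives 33.6 events, or 164 in total.

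**What 172 patients can detect with 80% power at two-sided 0.05.** Holding upfront CN at 72%, the pooled formula gives 78% power for 88.5% in the deferred arm and 81% for 89%. The detectable alternative is therefore about 88–89%.

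**Losses.** No rate is stated. If 10% were lost (an assumption), 77.4 per arm would remain. Power would then be 64.0% (pooled), 65.3% (unpooled), 67.6% (Schoenfeld) or 62.5% (Freedman).

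**The case against.** The strongest objection is that the protocol names no test, so the origin of 86 cannot be established and the one-sided explanation is conjecture. Ordinary rounding up of 86.5 gives 87 per arm (174), not 86. Other routes do reach 172 at two-sided 0.05. For example, 43 events / 0.25 = 172. Alternatively, 43 / 0.28 = 154, or 77 per arm, and 77 / 0.9 = 85.6 after a 10% loss allowance.

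This stands as far as the cause goes: the one-sided reading is a plausible inference and no more. It does not rescue the 80%. A 25% event fraction would need about 18.9 months of mean follow-up under the stated rates, which conflicts with the fixed 15 months. Dividing by 0.28 applies the upfront arm's event rate to both arms, although the design assumes 0.13 in the other.

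A second objection is that a loss allowance and the choice of formula commonly belong in an SAP, which is not at hand. That is accepted: their absence is not part of the finding. It also cannot be said that 172 contains no allowance, only that none is stated. If it does contain one, fewer patients would be evaluable and power would be lower still.

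A third objection is that proportions are the wrong basis for a time-to-event endpoint. The log-rank formulas and the simulation give essentially the same answer.

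**Conclusion.** The concern holds. The stated sample size, event-free rates, power and two-sided alpha are mutually inconsistent. At two-sided 0.05, power with 172 patients is about 70%: 67% to 72% by the usual two-proportion and log-rank formulas, and 69.8% by simulation. The size needed for 80% is 208 to 234 in total before any losses, depending on the formula. The log-rank figures assume proportional hazards, the simulation assumes exponential PFS, and all the main figures assume complete 15-month follow-up. No method tried brings two-sided power closer than about 8 percentage points to 80%. Either the power or the alpha in the sentence is wrong as written. Which one the sponsor intended cannot be determined from the protocol.

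**What to change.** Rewrite the Sample Size paragraph so that its figures agree. Without changing enrolment, it could state that 172 participants, with about 35 PFS events expected by 15 months, give about 70% power for 72% versus 87% 15-month PFS (hazard ratio 0.42) at two-sided 0.05, and that 80% power is reached only for 72% versus about 88–89%.

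If the calculation was one-sided at 0.05, the paragraph should say so and correct the alpha. The sponsor should then justify a one-sided test at that level, since the protocol labels both arms experimental.

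If 80% power at two-sided 0.05 is to be kept for the stated rates, the total has to rise to about 208–234 before losses.

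In each case it would help to name the formula and the event count, so that the figure can be reproduced.

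The first two options cost one paragraph and no patients, at the price of a less favourable power or alpha statement. The third adds about 36 to 62 patients (208 − 172 and 234 − 172).
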